11.1.2 Protocol Deviations

Protocol deviations are defined as those deviations from any procedure as defined in this document, including but not limited to, as any violation of inclusion/exclusion criteria, use of any nicotine or tobacco-containing product other than the assigned product during each of the exposure period, use of any nicotine tobacco-containing product during wash-out periods, assessments not performed or performed outside the scheduled time windows, or use of estrogen or other drugs that are known to affect CYP2A6 activity.

All protocol deviations will be documented appropriately in an approved format.

Information from the source documents will represent the primary source of protocol deviations. Information following site monitoring and other manual reviews will be documented in the site visit reports, follow-up letters, audit documentation, or other manual review and will be recorded and tracked in an approved format. Telecommunications and other verbal communications regarding deviations will be considered and handled as important communication, documented and tracked as protocol deviations, as necessary.

Data and information contained in this document are considered to constitute trade secrets and confidential commercial information, and the legal protections provided to such trade secrets and confidential information are hereby claimed under the applicable provisions of US law. No part of this document may be publicly disclosed without the written consent of PMI.

Individual entries for protocol deviations that are recorded following site monitoring and other manual reviews, will be reviewed against the individual data points in the CRF database but will not be formally reconciled with the CRF database (e.g., their description or occurrence date). The overall procedure for managing protocol deviations are described in the SOPs of the CRO Data Management Team. All deviations will be reviewed periodically, as determined at study start, to identify trends to improve monitoring and/or potential impact on the statistical analysis.

11.2 Data Handling

All study data will be managed by the Data Management Team at the CRO. The overall procedures for quality assurance of clinical study data are described in the SOPs of the CRO Data Management Team. The Data Management Team at the CRO will prepare a Data Management Plan, to be reviewed and approved by the Sponsor, prior to the start of the study. This document will describe, in detail, the procedures and processes related to Data Management.

All data of all subjects successfully enrolled, as well as subjects who failed screening, and/or experienced an AE during the study (from time of signing the informed consent form to the end of the passive safety FU), will be captured and stored in the study database.

All data collected during the study is property of the Sponsor, irrespective of the location of the database and the Data Management CRO.

11.2.1 Data Validation

The data will be validated as defined in the Data Management Plan and Data Validation Specifications. Discrepancy lists will be generated electronically, as necessary.

Data queries will be raised for discrepant or missing data. All changes to data will be captured in the database with a comprehensive audit trail.

11.2.2 Coding

Adverse events, medical/surgical history, and prior/concomitant medication will be classified according to the terminology of the latest version of the following Dictionaries, at time of coding the first entry:

Medical history:	Medical Dictionary for Regulatory Activities (MedDRA®)
Adverse events:	MedDRA®
Medications:	WHO Drug Dictionary Enhanced and Anatomical Therapeutic and Chemical classification system

11.2.3 Database Lock

When all outstanding Data Management issues have been resolved and all validation, quality review and cleaning activities are complete, the database or selected data is/are declared soft-locked. Access to change data in the soft-locked database or to change selected data at this time is limited.

After data review by the Sponsor, resolution of all raised queries and quality control of the changed data, the database or selected data thereof will be declared locked upon Sponsor approval, as applicable.

Any changes to the database after that time can only be made by written agreement between the Sponsor and the Data Management and Statistical Team at the CRO. Any of those changes must be documented in the database log file.

After study completion, the study database will be transferred to the Sponsor in the format specified in the Data Management Plan in the Clinical Data Interchange Standards Consortium Study Data Tabulation Model Data Structure Specifications.

12 PLANNED STATISTICAL METHODS

12.1 General Considerations

Full details of the statistical analysis will be given in a statistical analysis plan (SAP). Any changes to the planned statistical methods will be documented in the Clinical Study Report. The statistical evaluation will be performed using SAS[®], Version 9.3 or later.

12.1.1 Definitions for Statistical Data Analysis

Unless otherwise stated, for the purposes of statistical analyses, baseline is defined as the last available time point prior to T0 on Day -1.

Nicotine exposure parameters will be derived from plasma nicotine versus time data by NCA using Phoenix WinNonlin, Version 7.0 or higher. C_{max}, AUCs, and related PK parameters, as appropriate, will also be calculated. To minimize the potential bias in the nicotine plasma PK parameters for the fixed puffing regimens, background-concentration correction will be applied to the concentration data and derived PK parameters to adjust for carry-over effects. For nicotine exposure parameters, baseline (C₀) will be defined as the concentration immediately prior to T0 for each session. The baseline correction will be implemented by calculating the nicotine exposure parameters using adjusted concentration values as described below:

The nicotine terminal elimination rate constant λ_z (and $t_{1/2z}$) will be estimated from the Day 5 PK samples (or early termination samples, if available) using a linear regression on the log concentration the pre-T0 time points. The regression analysis should contain data from at least 3 different time points in the terminal phase (including the last quantifiable concentration but excluding the concentration at t_{max}), consistent with the assessment of a straight line on the log-transformed scale. The nicotine plasma background-corrected PK parameters will be derived by performing the NCA on the corrected concentrations.

For the purposes of background-correction of the plasma concentrations post-baseline the following formula will be applied: $cC_t = C_t - C_0 * e^{-\lambda_z t}$. Where, C_t is the corrected concentration at each time point, C_0 is the pre-use baseline concentration, λ_z is the Day 5 (or early termination, if available) terminal elimination rate constant and t is the actual time.

If plasma concentrations cannot be background-corrected in a sufficient number of subjects e.g., in the event that the λ_z (or $t_{1/2z}$) cannot be estimated, modelling approaches may be applied including conventional compartmental analyses. The total (untransformed) PK parameters will be reported and used for statistical analyses instead in case both correction methods are unsuccessful. If warranted, nonlinear mixed-effect modeling using nicotine pooled data across studies may also be used.

Additional nicotine PK parameters may be determined and reported in order to support the interpretation where appropriate.

A more detailed description of the analyses will be presented in the SAP.

Data and information contained in this document are considered to constitute trade secrets and confidential commercial information, and the legal protections provided to such trade secrets and confidential information are hereby claimed under the applicable provisions of US law. No part of this document may be publicly disclosed without the written consent of PMI.

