LSM	Least-squares means
mg	milligram
mL	Milliliter

Data and information contained in this document are considered to constitute trade secrets and confidential commercial information, and the legal protections provided to such trade secrets and confidential information are hereby claimed under the applicable provisions of US law. No part of this document may be publicly disclosed without the written consent of PMI.

MedDRA	Medical Dictionary for Regulatory Activities
M RTP	Modified risk tobacco product
ms	Millisecond
n	Number of subjects
NCA	Non-compartmental analysis
ng	Nanogram
NHANES III	National Health and Nutrition Survey III
PD	Pharmacodynamic(s)
PK	Pharmacokinetic(s)
PMI	Philip Morris International
PPM	Parts per million
QTcB	Corrected value of the interval between the Q and T waves on the electrocardiogram tracing, using Bazett's formula
QTcF	Corrected value of the interval between the Q and T waves on the electrocardiogram tracing, using Fridericia's formula
RCF	Relative centrifugal force
RRP	Reduced-Risk Product
SAE	Serious adverse event
SAP	Statistical analysis plan
SD	Standard deviation
SHM	Sample handling manual
SMP	Safety management plan
SOP	Standard Operating Procedure
SQ	Sensory questionnaire
T	Time point
T0	Time point of first product use during study day
t _{1/2}	Half-life
t _{max}	Time to maximum concentration
t _{peak}	Time to peak plasma nicotine concentration
UBC	United BioSource Corporation
ULN	Upper limit of the normal range
ULOQ	Upper limit of quantification
USB	Universal serial bus

Data and information contained in this document are considered to constitute trade secrets and confidential commercial information, and the legal protections provided to such trade secrets and confidential information are hereby claimed under the applicable provisions of US law. No part of this document may be publicly disclosed without the written consent of PMI.

VAS	Visual Analogue Scale
WBC	White blood cell (count)
WHO	World Health Organization
µg	Microgram

Explanation of Terms

The following special terms are used in this protocol:

CC	The term 'cigarette' refers to manufactured and commercially available cigarettes and excludes hand-rolled cigarettes, cigars, pipes, bidis, and other nicotine-containing products.

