7.7.4 Cough Assessment

Subjects will be asked if they have experienced a need to cough within 30 minutes after P4M3-1.7% product test at Admission (Day -2) and within 30 minutes after each fixed puffing regimen and *ad libitum* use on Days -1 to 4, and at discharge or at early termination. If the answer is 'yes', they

will be asked to complete a cough assessment questionnaire (which includes a VAS, three Likert scales, and an open question).

The VAS will assess how bothersome cough is to the subject ranging from 'not bothering me at all' to 'extremely bothersome'.

Furthermore, subjects will be asked to assess the intensity and frequency of cough and the amount of sputum production on Likert scales:

- The intensity of cough will be assessed on a 5-point Likert scale ranging from 1 to 5:
1 = very mild; 2 = mild; 3 = moderate; 4 = severe; 5 = very severe.
- The frequency of cough will be assessed on a 5-point Likert scale ranging from 1 to 5:
1 = rarely; 2 = sometimes; 3 = fairly often; 4 = often; 5 = almost always.
- The amount of sputum production will be assessed on a 4-point Likert scale ranging from 0 to 3:
0 = no sputum; 1 = a moderate amount of sputum; 2 = a larger amount of sputum;
3 = a very large amount of sputum.

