9.2 Admission Day -2

The following assessments will be performed at admission (Day -2) (Table 6):

Table 6. Event Schedule – Day -2 Admission

Blood sample	Procedures	Additional information
	Recheck of selected inclusion/exclusion criteria	
	Urine pregnancy test for female subjects	Pregnancy test results are to be available prior to P4M3 product test
√	Clinical laboratory parameters (hematology, urine analysis, clinical chemistry)	Fasting state
	Urine cotinine screening test	
	Urine drug screen	
	Breath alcohol screen	
	CO breath test	
	Vital signs	At least 5 minutes in supine position prior to measurement
	Physical examination	
	Breakfast	
	Debriefing on P4M3	
	Enrollment	
√	Trans -3'-hydroxycotinine and cotinine (CYP2A6 activity) in plasma	To be performed post enrollment and prior to product test
	P4M3 product test with HPT	Product test with P4M3-1.7% ad libitum for a maximum of 10 minutes.
	Assessment of cough (VAS, three Likert scales and one open question)	Completed by the subject on site within 30 minutes of product use
	Vital signs	At least 5 minutes in supine position prior to measurement, to be conducted at 60 minutes ± 10 minutes post end of product use
	Evening meal	
	Snack	
	Support during periods of abstinence from nicotine usage as required	All day as required
	AE/SAE recording, concomitant medication	All day

Abbreviations: AE = Adverse event; BMI = Body mass index; CYP2A6 = Cytochrome P450 2A6; SAE = Serious adverse event

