12.1.3 Handling of Missing Values and of Values outside the Detection Limits

In general, missing data will not be imputed in this study, due to the nature of the measurements and the short periods of exposure and use. However, for questionnaire data total scores and domain or subscale scores may use a certain degree of imputation by averaging across individual item scores. Further details will be provided in the SAP.

In general, for the estimation of PK parameters, values below the lower limit of quantification (LLOQ) will be treated as missing and will be ignored in the PK evaluation.

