12.3.3 Safety Population

The safety set population, consists of all the subjects who give informed consent and have at least one exposure to P4M3 (including the product test at Admission [Day -2]).

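### With no cough exception to the default baseline, the cough change score is taken against a post-use record and is undefined for new-onset cough unless a 'no' is coded (separately, minor: two different craving models)

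*Protocol*

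**What the plan says.** **Baseline.** Section 12.1.1 gives a general definition, subject to being stated otherwise: "baseline is defined as the last available time point prior to T0 on Day -1". The same section writes an explicit session-level exception for nicotine concentrations. It writes none for cough. T0 has two meanings. The abbreviation list has "Time point of first product use during study day"; sections 4.1 and 6.3.2 define it as the first puff of each session.

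**Cough schedule.** Section 7.7.4 starts the assessments on Day -2: "Subjects will be asked if they have experienced a need to cough within 30 minutes after P4M3-1.7% product test at Admission (Day -2". They continue after each session on Days -1 to 4 and once at discharge or early termination. Table 6 gives the Day -2 timing as "Completed by the subject on site within 30 minutes of product use". Screening (Table 5) has no cough assessment. Section 12.3.3 counts the product test as exposure: the safety population needs subjects who "have at least one exposure to P4M3 (including the product test at Admission [Day -2".

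**Cough scales.** Under 7.7.4, subjects who answer 'yes' to a need to cough "will be asked to complete a cough assessment questionnaire (which includes a VAS, three Likert scales, and an open question". Intensity runs "1 = very mild; 2 = mild; 3 = moderate; 4 = severe; 5 = very severe", and frequency also starts at 1, for rarely. Only sputum has a zero. Section 12.1.3 says that, in general, "missing data will not be imputed in this study". Sections 3.2 (objective 7) and 12.6.3 call for change from baseline.

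**Craving.** The synopsis model has the value before product use as baseline, product by time point, and a random subject effect, but no time point main effect. Section 12.6.2.1 has an unqualified baseline value and a time point main effect, and names no subject effect.

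**The concern.** A baseline for a tolerability symptom should describe the subject before the exposure of interest. Here no cough record precedes all product use. On one reading of T0 the reference is itself a test variant. On the other, for ad libitum sessions, it is own-product fixed puffing, so an ad libitum change score mixes regimen with product.

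The questionnaire gate adds a second problem. A change score needs a score at both ends, and a score needs a 'yes'. The subject of most interest, who did not cough at baseline and coughs on a later variant, has nothing to subtract from. Section 7.7 adds that symptoms documented on questionnaires need not also be recorded as adverse events, so the adverse event tables are not a guaranteed backstop.

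For craving, one endpoint has two stated models, and which is used affects the covariate and the rule for dropping the interaction.

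**Working it through.** **Step 1: which record is the baseline?** The schedule has 1 assessment after the Day -2 test, 5 days × 2 sessions = 10 after the sessions on Days -1 to 4, and 1 at discharge: 12 in all.

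| Reading of T0 on Day -1 | Cough records before it | Last one (baseline) |
|---|---|---|
| First use of the day (abbreviation list) | 1 | After P4M3-1.7% test, Day -2 |
| Per session, fixed puffing (4.1, 6.3.2) | 1 | After P4M3-1.7% test, Day -2 |
| Per session, ad libitum (4.1, 6.3.2) | 2 | After own-e-cigarette fixed puffing, Day -1 |

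All rows give a post-use baseline.

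**Step 2: who has a change score?** If a 'no' leaves the scales empty and nothing is imputed, a subject needs a 'yes' at baseline and at the later session. The questionnaire exception in 12.1.3 averages across items, and a 'no' leaves no items to average.

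The protocol gives no cough rates, so these are assumed. Let p be the probability of 'yes' at each of the two assessments, φ the within-subject correlation of the answers, and n = 16 randomised.

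- Coughers at the later session: n·p
- With a change score: n·[p² + φ·p(1−p)]
- Share of those coughers without one: (1−p)(1−φ)

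| p | Coughers of 16 | With change score, φ = 0 | Share without | With change score, φ = 0.5 | Share without |
|---|---|---|---|---|---|
| 0.2 | 3.2 | 16 × 0.040 = 0.6 | 80% | 16 × 0.120 = 1.9 | 40% |
| 0.3 | 4.8 | 16 × 0.090 = 1.4 | 70% | 16 × 0.195 = 3.1 | 35% |
| 0.5 | 8.0 | 16 × 0.250 = 4.0 | 50% | 16 × 0.375 = 6.0 | 25% |

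With the 12 subjects targeted for analysis, the counts with a change score are 0.5, 1.1 and 3.0 (φ = 0), or 1.4, 2.3 and 4.5 (φ = 0.5).

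Rates may also differ between the assessments. With 25% coughing at baseline, 50% later and independence, 16 × 0.5 = 8 cough later and 16 × 0.25 × 0.5 = 2 have a change score. Over baseline rates of 10% to 50%, later rates of 25% to 50% and φ from 0 to 0.3, the share without one runs from 24% to 90%.

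**Step 3: what is unaffected?** Among subjects with a baseline score, the same value is subtracted from every session of a regimen. It cancels from variant-minus-own differences.

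**Step 4: craving.** There are 5 products (own e-cigarette and four variants) and 7 post-T0 time points per regimen. The ranks below are for the product and time terms.

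| | Synopsis | 12.6.2.1 |
|---|---|---|
| Rank with interaction | 35 | 35 |
| Rank without interaction | 5 | 11 |
| Interaction df tested | 35 − 5 = 30 | 35 − 11 = 24 |

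With the interaction kept, the two describe the same product-by-time means. If it is dropped under the p > 0.1 rule, the synopsis model has no time effect left. In the synopsis that rule also tests time and interaction together, because time enters only through the interaction.

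**The case against.** **T0 is per session in the operative text.** This stands in part. Sections 4.1 and 6.3.2 define it so, and 12.1.2 requires summaries by regimen. A reader might infer that cough is always measured against P4M3. The documents do not support that for ad libitum sessions, where the reference may be own-e-cigarette use. It is still post-use.

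**A skipped scale is not a missing value.** This also stands in part. A 'no' is a recorded answer, 12.1.3 speaks only in general, and the statistical analysis plan may code a 'no'. The gap in change scores is what follows if nothing is coded; it is not a stated rule to discard. The gate is explicit only in 7.7.4: Tables 6 to 8 and Appendix 1 list the assessment without repeating it.

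**New-onset cough is visible elsewhere.** True. Actual values, yes/no answers and listings keep it. Section 7.7 lets the investigator record such symptoms as adverse events and makes the open interview the main source of them. A reader might infer that the study would hide new-onset cough or bias product comparisons. Neither follows; the loss is confined to the change-from-baseline summary.

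**The analysis plan can settle all this.** It can. But 12.1.1 already fixes a default, makes an exception for nicotine, and makes none for cough. Followed as written, that rule gives a poor result.

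**On craving,** the unqualified baseline in 12.6.2.1 may simply abbreviate the synopsis wording, and pre-use craving is collected before every session (7.7.3). That is plausible, so it should not be asserted that a Day -1 covariate is planned. The difference in time and subject terms remains.

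**Conclusion.** The point holds in limited form. As the protocol stands, the cough change from baseline uses a post-use reference on either reading of T0. It is undefined for a subject who first coughs at a later session, unless a 'no' is given a code.

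At equal assumed cough rates of 20% to 50%, between a quarter (rate 50%, correlation 0.5) and four fifths (rate 20%, independence) of later coughers have no change score. The summary would then rest on about 0.6 to 6.0 of 16 subjects. These figures depend on assumed rates and correlations and on a 'no' being left uncoded. The mechanism does not depend on the rates; the loss vanishes only if every later cougher also coughed at baseline.

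The consequence is modest. Cough is one descriptive item under a secondary safety objective, adverse events are the primary safety assessment, and the study tests no hypothesis. It still merits correction because the named endpoint would miss the event it is meant to show.

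The craving mismatch is real, minor and separate. It matters mainly if the interaction is removed.

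**What to change.** **Cough.** State a cough exception to the default in 12.1.1 and carry it into 3.2 and 12.6.3:

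- Summarise the yes/no need-to-cough answer for every subject and session, and compare each variant with the own-e-cigarette session of the same regimen on Day -1.
- Code a 'no' as a separate no-cough category (0) below the 1 to 5 intensity and frequency scales, so that non-coughers are counted without being merged with the lowest cough level.
- Summarise the bothersomeness VAS and the sputum score among coughers, showing the number of non-coughers beside them.
- Report the discharge or early-termination assessment descriptively, without a change score, since it has no matching regimen on Day -1.

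**Craving.** State one model in both the synopsis and 12.6.2.1: same-session pre-use VAS, product, sex, time point, product by time point, and subject as a random effect.

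**Cost.** Wording and programming only. The cough answer after each session and the craving score before each session are already collected.

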4.2 Rationale for Study Design

The goal of the study will be to select the P4M3 variant(s) that result(s) in nicotine absorption close to that observed with subjects' own e-cigarettes. The nicotine plasma concentration profiles and derived PK parameters, subjective and behavioral effects, and HPT parameters of P4M3 variants and subjects' own e-cigarettes will be evaluated. The concentrations of nicotine in some of the P4M3 variants tested in this study are already available on the market and exposure of the IPs will be to experienced e-cigarette users aged 21 - 65 years (inclusive) following a single-use experience with fixed puffing in the morning and after *ad libitum* use of P4M3 in the afternoon across 4 days. Subjects with a history of e-cigarette use were chosen for this study based on data from previous studies indicating that having previous experience using such products may impact nicotine exposure and puffing topography (Farsalinos 2013, 2015; Spindle 2015). Further, the use of fixed and *ad libitum* puffing regimens by experienced consumers is expected to provide insight into nicotine delivery by the products that is possible under consistent use conditions across subjects (fixed puffing regimen) as well as a means to assess the products' ability to meet a consumers needs during short-term "real-life" use conditions (*ad libitum* regimen).

Plasma nicotine presents a biphasic profile, with a typical rapid initial disposition half-life ($t_{1/2\alpha}$) of 1.35 hours, followed by a slower terminal elimination half-life ($t_{1/2z}$) of 17 hours (Marchand et al, 2017). To ensure a full nicotine washout between each product use, a separation of 3 days would be required ($\sim 5 \times$ elimination $t_{1/2z}$). Due to the impracticality of undergoing long periods of abstinence for smokers, shorter washout periods have been selected. To minimize the potential bias in the nicotine plasma PK parameters for the fixed puffing regimens, background-concentration correction will be applied to adjust for carry-over effects. The simplest approach by which this can be achieved requires a) a minimum washout-out period of 10 hours prior to each fixed puffing regimen session (this ensures that subjects have entered the terminal elimination phase of nicotine) and b) the estimation of $t_{1/2z}$ (or the terminal elimination rate constant λ_z) on Day 5 for each subject.

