9.4 Day of Discharge

The following assessments will be conducted prior to the time of Discharge on Day 5 (Table 9):

Table 9. Event Schedule – Day 5 Discharge

Blood sample	Procedures	Additional information
	Optional morning snack	
	AE/SAE recording, concomitant medication	All day
	Assessment of cough (VAS, three Likert scales and one open question)	
√	Clinical laboratory parameters (hematology, urine analysis, clinical chemistry)	This laboratory assessment will be performed on the morning of Day 5 under fasting conditions
	Washout	Needs to be maintained
√	Plasma samples for determination of subject's nicotine $t_{1/2z}$	Post T0 (start of the last product use), blood will be drawn at the following time points: T1 after 14 hours ± 30 minutes, T2 after 16 hours ± 30 minutes, T3 after 18 hours ± 30 minutes, T4 after 20 hours ± 30 minutes, T5 after 24 hours ± 30 minutes.
	Urine pregnancy test for female subjects	
	Vital signs	At least 5 minutes in supine position prior to measurement
	ECG	At least 10 minutes in supine position prior to recording
	Spirometry without short-acting bronchodilator	
	Physical examination	
	Support during nicotine abstinence as required	All day as required
	Debriefing on IP	
	Time of discharge	

Abbreviations: AE = Adverse event; ECG = Electrocardiogram, SAE = Serious adverse event, VAS = Visual analogue scale, Adapted mCEQ = Adapted version of the modified Cigarette Evaluation Questionnaire, SQ = Sensory questionnaire

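### The last fallback in Section 12.1.1 analyses uncorrected nicotine parameters, discarding the measured pre-use concentration that supplies most of the correction (minor)

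*Protocol*

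**What the plan says.** Section 4.2 of the protocol explains that full washout would need about 3 days, that shorter washouts were chosen, and that "background-concentration correction will be applied to adjust for carry-over effects". It describes plasma nicotine as biphasic, with a "typical rapid initial disposition half-life ($t_{1/2\alpha}$) of 1.35 hours", "followed by a slower terminal elimination half-life ($t_{1/2z}$) of 17 hours".

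Section 12.1.1 gives the correction: the corrected concentration at time t is the observed concentration minus C0·exp(−λz·t). C0 "will be defined as the concentration immediately prior to T0 for each session". λz is the subject's own terminal rate, fitted to the Day 5 samples, or to early termination samples if there are any. Table 9 (Section 9.4) starts the Day 5 series with "T1 after 14 hours ± 30 minutes" and ends it at 24 hours, five samples in all.

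The fallback has steps. It begins "If plasma concentrations cannot be background-corrected in a sufficient number of subjects", with a λz that cannot be estimated as the example. Modelling, including compartmental analysis, may then be applied. The last step reads: "The total (untransformed) PK parameters will be reported and used for statistical analyses instead in case both correction methods are unsuccessful". A further sentence allows pooled mixed-effect modelling across studies, if warranted. Section 12.8 leaves the alternative models to the SAP.

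**The concern.** The correction has two inputs: a measured C0 for each session and a rate λz for each subject. The stated reason for failure is loss of the rate. Yet the final step abandons both inputs and analyses values that still contain all of the carry-over that Section 4.2 says must be removed. No listed step keeps the measured C0 with a rate borrowed from other subjects or from the half-life the protocol itself cites.

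At stake are the variant:own ratios with 90% confidence intervals (Section 12.6.2) and the parallel ad libitum analyses (Section 12.5.2). The study's purpose is to pick variants whose nicotine absorption is near that of the subject's own product, so a distortion of these ratios bears directly on the choice.

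**Working it through.** The protocol gives no figure for the background or for the effect of the fallback, so there is nothing to reproduce.

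**Inputs.** From the protocol: half-lives of 17 h and 1.35 h (Section 4.2), a 4 h sampling window (Section 7.4.1), and a washout of at least 10 h. Assumed: C0 as a fraction c of own-product cCmax (5% to 40%), and a corrected profile that falls from its peak with the 1.35 h half-life.

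**1. How much of the correction is C0?** λz = ln2/17 = 0.0408 per h.
- Share of C0 subtracted: exp(−0.0408 × 1/6) = 0.993 at 10 minutes; exp(−0.0408 × 4) = 0.850 at 4 h.
- Background AUC(0-4h) = C0 × (1 − exp(−4λz))/λz = 3.69·C0. Undecayed C0 would give 4.00·C0, and 3.69/4.00 = 0.92.
- Half-life wrong by a factor of two: 3.41·C0 at 8.5 h and 3.84·C0 at 34 h, a change of −8% and +4%.
- Extreme case, 4 h: 2.89·C0, or −22%.
- After 10 h, 10/1.35 = 7.4 initial half-lives have passed and 0.6% of the fast phase is left, so C0 lies in the terminal phase.

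**2. Effect of total values, equal backgrounds.** Own cAUC = cCmax × (1 − exp(−4·ln2/1.35))/(ln2/1.35) = 1.698·cCmax. The total ratio for a true ratio r is (1.698r + 3.691c)/(1.698 + 3.691c). For r = 0.50:

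| c | Total AUC ratio |
|---|---|
| 5% | 0.55 |
| 10% | 0.59 |
| 20% | 1.587/2.436 = 0.65 |
| 40% | 0.73 |

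At c = 20%, a true 2.0 becomes 4.134/2.436 = 1.70.

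**3. Same setting (c = 20%, r = 0.50), C0 kept with a wrong rate.** The uncorrected remainder is c times the difference in background factor.
- 8.5 h used: 0.2 × (3.691 − 3.413) = 0.056; (0.849 + 0.056)/(1.698 + 0.056) = 0.52.
- 34 h used: 0.2 × (3.691 − 3.841) = −0.030; 0.819/1.668 = 0.49.
- 4 h used: 0.2 × (3.691 − 2.885) = 0.161; 1.010/1.859 = 0.54, still nearer the truth than 0.65.

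**4. Unequal backgrounds, c = 20%, true ratio 1.00.**
- Variant background 1.5 times own: (1.698 + 1.107)/2.436 = 1.15.
- Variant background half of own: (1.698 + 0.369)/2.436 = 0.85.
- A true 1.20 with the 1.5-fold background: (2.038 + 1.107)/2.436 = 1.29.

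**5. Exposure-normalised Cmax** (also planned for fixed puffing). True normalised ratio 1, variant exposure twice own, equal backgrounds of 25% of own cCmax: [(2 + 0.25)/2]/(1 + 0.25) = 0.90.

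**6. How often is λz lost through a poor slope?** For samples at 14, 16, 18, 20 and 24 h, Sxx = 59.2 and SE = σ/√59.2. With assumed residual error of 10% or 20%, the CV of λz is 32% or 64%. A non-positive slope then occurs in 0.09% or 5.8% of subjects, about 0.01 or 0.9 expected among 16.

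**The case against.** The strongest reply is that this branch is remote. Total values are used only after correction has failed in a sufficient number of subjects and modelling has failed as well. Step 6 shows that outright slope failure should be rare. That stands, and it sets the severity. A reader might infer from the short 14 to 24 h window that the fallback is likely to be invoked. At those error levels about 6% or 28% of fitted half-lives would fall outside 8.5 to 34 h, but most of those are positive slopes. λz has then been estimated, and Section 12.1.1 sets no plausibility window. The branch is not empty, though. Section 12.2 allows for up to 25% of subjects with incomplete data, and λz for early terminators rests on samples taken if available. The heading in Section 7.4.1 mentions an early termination visit, but its times count from Day 4 use, and Table 10 lists no plasma nicotine sample.

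A second reply is that pooled mixed-effect modelling could lend a rate to subjects without their own, and that the SAP may define it. This is fair, but the sentence is optional. It does not displace the stated rule that total values enter the analyses.

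Third, no hypothesis is tested, no closeness margin is set, and the ad libitum model adjusts for the trough, which may absorb part of the background there. All true. The fixed-puffing model has no such covariate.

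A reader might also infer that completers lacking λz lose every corrected parameter. The protocol does not say so, and single-subject handling may be in the SAP.

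**Conclusion.** The concern holds as a minor one. Section 12.1.1 fixes a last step that drops a measured C0 because a rate of small influence is missing. At 17 h, C0 carries about 92% of the AUC(0-4h) correction and about 99% at 10 minutes.

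It is tempting to say that total values pull every variant:own ratio toward 1 and so favour declaring variants close. The design does not support that. The pull is toward the ratio of the backgrounds. Own product is always used on Day -1, after whatever preceded admission and the Day -2 product test, while each variant follows the previous day's ad libitum session, so equal backgrounds cannot be presumed. Steps 4 and 5 show movement away from 1. What can be said is that the bias is toward 1 when backgrounds are alike and of unknown direction otherwise. That makes total values harder to interpret.

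The sizes rest on the assumed C0 fraction, a single-phase decline and no covariate adjustment. The conclusion about λz rests on the 17 h half-life; it weakens for AUC if true half-lives are very short.

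**What to change.** In Section 12.1.1, and in the SAP to match, insert a step before any use of total values. For any subject without an estimable λz, early terminators included, apply the same formula with that subject's own session C0 and the median λz of the other subjects. If no subject has an estimable λz, use ln2/17 h from Section 4.2. Report total parameters descriptively and delete their use for statistical analysis; Section 12.5.1 already presents unadjusted ad libitum parameters.

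The cost is a sentence or two and no extra samples. The downside is a small error from the borrowed rate: about 0.02 or less on a ratio of 0.50, with C0 at 20% of own cCmax, equal backgrounds and a half-life wrong by a factor of two. A session whose C0 is missing or below the quantification limit still needs its own rule.
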